to where 70%-80% of peak work rate was identified will be used. After sufficient rest, an additional constant work rate test will be given using increases in speed with a level treadmill to determine the speed that elicits a VO_2 comparable to the previous walking test. In addition, subjects will be asked to a series of questionnaires to characterize their disease state. During the third and fourth visits, airflow, respiratory rate, oximetry, dynamic hyperinflation, and walking cadence will be recorded during the trials at the speed/no slope or speed/slope determined in the previous visit. Speed or slope conditions will be randomized across visits. At the end of each trial, dyspnea rating will be recorded.

C.2 Subjects, Sample Size, and Inclusion Criteria

C.2.a Sample size justification: For this proposal, we are requesting funding to recruit and enroll a pilot population of 25 subjects. Subjects will be recruited and screened until all 25 subjects are enrolled. Stratified sampling will be conducted as subjects are enrolled. Subjects will be stratified by disease severity (Table 1). According to Omaha VAMC patient numbers, more than 45,000 visits are documented in the pulmonary clinics and other general health clinics with over 2,000 pulmonary function tests yearly. We anticipate recruiting 3-4 subjects/month during months 3-18. We anticipate meeting our enrollment goal of 1-2 enrolled/month.

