Subjects will be outfitted with a face mask that covers their nose and mouth attached to a portable metabolic cart (K5, Cosmed USA, Inc., Chicago, IL). We previously have used this method to measure energy expenditure in COPD patients without reported adverse events. Resting heart rate, respiratory rates, and tidal volume will be recorded as well through this device. Subjects will stand quietly for five minutes while energy expenditure is collected through the metabolic unit. Subjects will have a transcutaneous oximeter attached to their abductor pollicis brevis (The Moxy Monitor System, Moxy, Minneapolis, MN). Subjects will walk at the speed and slope that corresponds to 70%-80% peak work rate. Subjects will maintain this level of exercise for one minute. If fatigued, they will be instructed to stop. (As exercise time at 80% VO₂ max is generally six minutes, we anticipate most subjects will complete the test without difficulty.) After sufficient rest and the return of heart rate and respiratory rate to resting levels for at least 10 minutes, subjects will complete an additional constant work rate test. They will walk at increasing speeds until the same VO₂ from the previous walking test is achieved. This speed will be recorded, and the subject will be asked to continue to exercise at this rate for one minute.

C.3.c VISIT 3: Within seven days, subjects will return for their first experimental visit. Subjects will be prepared for data collection by wearing a form-fitting suit (i.e., wrestling singlet) and obtaining height and body weight. Retro-reflective markers will be placed bilaterally on anatomical locations of the feet, legs, and hips (Figure 5),

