in addition to 89 markers on the thorax and abdomen.⁶⁶⁻⁶⁹ Subjects will be outfitted with the portable metabolic cart and oximeter as in the previous visit. One of two treadmill trials will be performed: 1) at the speed and 2) at the slope +speed determined in the previous visit. Trial order will be randomized among subjects and across visits 3 & 4. For each trial, subjects will be asked to walk on a treadmill for up to 6 minutes. Speed or slope will be increased every 30 seconds and they will be asked to walk for one minute at that speed or slope. Once they reach the speed or slope that was determined to be 70%-80% of peak work rate, they will walk for an additional one minute. This procedure will allow for multiple data points for interpolation. Immediately at the end of the trial, dyspnea will be assessed by Borg scale.⁷⁰ Dynamic hyperinflation will be assessed through motion capture of the thorax and abdomen (optoplethysmography).⁶⁶⁻⁶⁹

C.3.d VISIT 4: Within seven days, subjects will return for their last experimental visit. Methods will be similar to C.3.c. Subjects will complete the treadmill trial that was not completed in Visit 3, either the

Figure 5. Subject wearing form-fitting suit while walking on a level treadmill.

speed or the slope trial. The treadmill trial will be administered in the same manner between both visits.

C.4 Instrumentation and Data Processing Measures (Table 2): C.4.a Questionnaires to be used as covariates

Chronic Respiratory Disease Questionnaire:^{62, 63} A 20-item questionnaire in which items are scored from 1 (most severe) to 7 (no impairment). There are four subscale areas tested: dyspnea, fatigue, emotion, and mastery. In the dyspnea section, the subject is asked to recall the five most important activities that caused dyspnea over the past two weeks. Items within each subsection can range from 1 to 7 or most severe to no impairment. A total score, as well as individual subscale scores, can be calculated.

SF-36:⁶⁴ A generic assessment of health-related quality of life from the subject's perspective. The SF-36 contains eight domains: physical functioning, role-physical, general health perceptions, vitality, social functioning, role-emotional, mental health, and health transition. Two composite scores result: physical health composite score and mental health composite score. Scores >50 indicate better physical or mental health than the mean and <50 indicate worse health.²²

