NOTE: mMRC=modified British Medical Research Council Questionnaire; CAT=COPD Assessment Tool

surface of the trunk (Motion Analysis Corp., Santa Rosa, CA; 120Hz). The volume of the trunk enclosed by the surface will be obtained through a custom computer code (MathWorks, Inc., Natick, MA). Dynamic hyperinflation will be considered to be present when end-expiratory chest wall volume increased in relation to resting values.^{75, 84}

Perceived dyspnea:⁷⁰ Breathlessness will be measured based on a 0 to 10-point Borg scale at the end of the treadmill trials.

C.4.c Aim 2: Compare differences in respiratory rate, oxygen uptake, and lung dead space from speed to slope walking.

Respiratory rate: Respiratory rate will be analyzed using motion capture markers on the chest. With custom computer code, the markers will be identified to model a sphere. The volume of the sphere will be recorded over time. As the volume increases and decreases, respiratory flow will be identified, and respiratory rate can be calculated.

Oxygen uptake: Heart rate and pulmonary gas exchange analysis will be recorded on a breath-by-breath basis (TrueOne2400; ParvoMedics, Sandy, Utah). This will provide an accurate measure of pulmonary gas exchange, including oxygen uptake, i.e. VO₂, in real-time. Steady-state VO₂ while walking will be averaged and normalized to standing metabolic rate. Heart rate is recorded via an interface with a Polar heart rate monitor and is synchronized to pulmonary gas exchange.

Dead space: Tidal volume and expired carbon dioxide will be measured using the same equipment as oxygen uptake above. Partial pressure of arterial carbon dioxide will be measured using a transcutaneous sensor (The Moxy Monitor System, Moxy, Minneapolis, MN). Dead space is equal to tidal volume multiplied by the partial pressure of arterial carbon dioxide (PaCO₂) minus partial pressure of expired carbon dioxide (PeCO₂) divided by PaCO₂.

C.4.d Aim 3: Determine the complexity of walking and breathing coupling ratios between speed v. slope walking.

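### Aim 2 takes respiratory rate from a chest-marker sphere with no stated breath-detection rule or airflow check, although the mask system worn in the same trials separates each breath

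*Combined protocol and SAP*

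**What the plan says.** Section C.4.c (Aim 2, Respiratory rate) names the source: "Respiratory rate will be analyzed using motion capture markers on the chest". It continues: "With custom computer code, the markers will be identified to model a sphere". The rate then follows from the volume trace: "As the volume increases and decreases, respiratory flow will be identified, and respiratory rate can be calculated". That is the whole definition.

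Other sections describe a second possible source in the same trials:

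- C.3.c (Visit 3): "Subjects will be outfitted with the portable metabolic cart and oximeter as in the previous visit". C.3.d says that Visit 4 follows similar methods.
- C.1: "During the third and fourth visits, airflow, respiratory rate, oximetry, dynamic hyperinflation, and walking cadence will be recorded during the trials".
- C.4.c (Oxygen uptake): "Heart rate and pulmonary gas exchange analysis will be recorded on a breath-by-breath basis". The dead-space paragraph takes tidal volume from the same equipment.
- C.3.b (Visit 2), of the mask system: "Resting heart rate, respiratory rates, and tidal volume will be recorded as well through this device".

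Respiratory rate matters to the study. It is in the key hypothesis in A.2, and a significant decrease on slope is part of the Aim 2 criterion in C.5.

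**The concern.** The trunk does more than breathe during treadmill walking. If trunk deformation or marker wobble at step or stride frequency enters the sphere volume, a rule that counts rises and falls can record breaths that did not occur. The speed and slope trials are expected to differ in cadence (A.3, C.6), and they may differ in movement cycles per breath. Such miscounting therefore need not cancel in the within-subject comparison. Randomising trial order does not remove it, because it travels with the condition.

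The plan gives no safeguard for this signal. The only marker clean-up is in C.4.d, under Aim 3: spikes and points beyond three standard deviations are removed and splined. That would not remove a regular oscillation. C.4.b cites literature for the trunk volume enclosed by 89 markers, but C.4.c cites none for the sphere.

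At stake is whether an Aim 2 difference, or the lack of one, reflects breathing or the way breaths were counted.

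**Working it through.** The plan gives no figure to reproduce. There is no artefact size, no expected rate difference, and no SD.

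**Step 1: is a flow-derived rate available during walking?** The C.3.b sentence opens with resting values at Visit 2, so it does not settle the matter. C.1 lists airflow and respiratory rate during the trials without naming the instrument. The inference rests on C.3.c and C.3.d (mask system worn at both experimental visits) together with C.4.c (breath-by-breath gas exchange, and tidal volume from the same equipment). Both measurements require breaths to be separated. Availability is therefore a well-supported inference rather than an explicit statement.

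**Step 2: when would movement create false breaths?** Illustrative model: volume = sin(t) + a·sin(kt + φ), where a is movement amplitude relative to breath amplitude, k is movement cycles per breath, and every local maximum of the unfiltered trace is counted. The smallest a that gives more than one peak per breath, over phases φ, is:

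| k | threshold a |
|---|---|
| 1 | about 1.0 |
| 2 | 0.26 to 0.51 |
| 4 | 0.07 to 0.18 |

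The governing quantity is cycles per breath, not cadence alone.

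**Step 3: which trial would be affected more?** Same model sampled at 120 Hz for one minute, a = 0.30, averaged over 24 phases. All rates are assumptions.

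| Trial | Movement/min | True breaths/min | k | Counted/min | Excess/min |
|---|---|---|---|---|---|
| Speed | 60 | 28 | 60/28 = 2.14 | 32.3 | 4.3 |
| Slope, same breathing rate | 50 | 28 | 50/28 = 1.79 | 28.0 | 0.0 |
| Slope, slower breathing | 50 | 24 | 50/24 = 2.08 | 28.0 | 4.0 |
| Slope, much slower breathing | 50 | 20 | 50/20 = 2.50 | 28.3 | 8.3 |

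- With equal true rates, a true difference of 0 is counted as 32.3 − 28.0 = 4.3.
- With 28 against 20, a true difference of 8 is counted as 32.3 − 28.3 = 4.0.

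The same artefact can create a difference or hide one. At a = 0.20, a movement component of 45 to 60/min adds no false breaths to breathing at 28/min.

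**Step 4: how much would a differential error matter?** Assume 25 pairs, a true difference of zero, two-sided α = 0.05, and an SD of paired differences of 3 breaths/min. A paired t-test with differential bias b has noncentrality (b/3)·√25.

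| b (breaths/min) | Noncentrality | P(p < 0.05) |
|---|---|---|
| 0.2 | 0.33 | 6% |
| 0.5 | 0.83 | 13% |
| 1.0 | 1.67 | 36% |
| 2.0 | 3.33 | 89% |

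For b = 1.0, changing the SD to 2 or 4 gives 67% or about 22%. The consequence runs from negligible to decisive according to a quantity the documents do not give.

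**The case against.** The artefact is conjecture. Nothing in the documents shows it. Rigid translation or rotation of the trunk does not change the volume of a fitted sphere, so deformation or marker wobble is needed. The protocol does not say that every local maximum will be counted; it only leaves the code undescribed. A modest rule, requiring a peak to stand out by 30% of the peak-to-peak range, holds the count at 27.5 to 28/min for breathing at 28/min, with a 45 to 60/min component up to 50% amplitude or a 90 to 120/min component up to 30%. It fails only at extremes (48 to 52/min counted at 120/min and 50%). All of this stands, and it limits the claim to an unguarded route for error.

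A reader might infer that the error inflates the faster level trial and so favours the hypothesis. The documents do not support that. The inference needs equal true breathing rates, or the same fraction of strides miscounted in both trials. The plan itself expects slower breathing on slope (C.6) and more complex coupling there (C.1). If that means more cycles per breath, the excess could be as large or larger on slope.

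A reader might also extend the point to Aim 3 and ask for breath timing from the mask. C.4.d does not say which signal supplies breathing rhythm. Motion capture also puts breath onset and heel strike on one clock, whereas a mask signal would need alignment. No change to Aim 3 is required here.

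Finally, in a 25-subject pilot the choice of instrument may look like preference. It is more than that: the marker rate has no stated detection rule or check, and a more direct measurement should already be in hand.

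**Conclusion.** The point holds as a cheap improvement to the definition of an Aim 2 outcome. It does not show that the result will be biased. C.4.c relies on an undescribed, unchecked marker signal where a flow-derived rate should exist for the same trials. Miscounting could differ by condition, but its size and direction are unknown. The thresholds and probabilities above rest on an unfiltered sinusoidal model and on assumed rates and SDs; they show a range of possibilities and do not estimate the error in this study.

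The conclusion assumes that the metabolic system yields usable breath timing during walking. One inconsistency bears on this: C.3.b names the K5, which C.3.c carries into the experimental visits, while C.4.c names the TrueOne2400 for oxygen uptake.

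**What to change.** In C.4.c:

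1. Define the Aim 2 respiratory rate as the flow-derived, breath-by-breath rate from the metabolic system, over the same analysis window as VO2.
2. Keep the marker-derived rate as a secondary check. State its breath-detection rule and how step and stride frequencies are handled, and report its agreement with the flow-derived rate separately for the speed and slope trials.
3. Reconcile C.3.b and C.3.c with C.4.c on which metabolic device supplies the data at Visits 3 and 4.

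No new measurements are needed if breath-by-breath data are recorded as described. The cost is some extra analysis work and reliance on complete mask data.

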The study will be divided into specific goals that will be targeted and achieved (Table 3). Every three months, intermediate objectives will be assessed, and decisions will be made regarding the course and direction of the continuing research effort. Table 3. Timeline Year 1 Year 2

C.8 Future Directions

In summary, our research proposal uses a novel theoretical approach and a shift in clinical research through a new method. By exploring an innovative approach to improving exercise

performance in COPD, it may be possible to increase exercise training intensity and duration and thus, improve the benefits of training during rehabilitation. Results from this study, including the demonstration of physiologic and symptomatic benefits from the proposed method of slope walking, will set the stage for a rigorous, well-powered, full Merit award outcome study evaluating the effectiveness of a slopebased training regimen as part of rehabilitation. This future Merit award clinical trial needs to demonstrate that physical activity and lung function, outcomes most associated with morbidity and mortality, improve after a sloped-based pulmonary rehabilitation approach.
